**Appendix 10: Screening questions to establish immune status for medical history**

- If answer Yes to (3), (4), (5), (7), should undergo immune blood tests before deciding if need to be excluded.
- If participant needs to have immune blood tests AND answers Yes to (1) and/or (8), consider deferring blood test until free from illness for 7 days / free from blood products for 3 months.
- If participant needs to have immune blood tests, please record all relevant history (i.e. to which question did they answer Yes) in the clinical background section of the pathology request slip.

1) **Has your child had an infection or a febrile (high temperature) illness within the last seven (7) days?**  Y / N

If Yes, and if sibling CBU in storage, consider deferring visit 2 blood test until free from illness for 7 days

2) **Has your child ever been diagnosed with an immune system disorder or immune deficiency syndrome?**

*If yes(Y), please specify:*

If Yes, exclude from participation

3) **Has your child needed to be admitted to hospital for intravenous (I.V.) antibiotics to clear an infection on more than two (2) occasions in their life?**

If Yes, consult with immunologist regarding blood test results before deciding to exclude

4) **Has your child ever needed two (2) or more months of oral antibiotics to clear an infection?**

If Yes, consult with immunologist regarding blood test results before deciding to exclude

5) **Has any Doctor or Maternal Child Health Nurse ever been concerned about your child being underweight?**

If Yes, consult with immunologist regarding blood test results before deciding to exclude

6) **Has your child ever been diagnosed with a genetic disorder such as Down syndrome, Di George syndrome etc?**

*If yes(Y), please specify:*

If Yes, exclude from participation

- 7) **Has any family member or relative of your child ever been diagnosed with an immune system disorder or immune deficiency syndrome?**

*If yes(Y), please specify:*

If Yes, consult with immunologist regarding blood test results before deciding to exclude

- 8) **Has your child received any blood products such as packed red blood cells, platelets, albumin or immunoglobulin in the last three (3) months?**

*If yes(Y), please specify:*

If Yes, and if sibling CBU in storage, consider deferring visit 2 blood test until free from blood products for 3 months

- 9) **Was your child born prematurely, before 36 weeks' gestation?**

Appendix 12: Serious adverse event report form

# SAE REPORT FORM (Individual Reports)

Internal\* SAEs (occurring to RCH participants) **must be reported to the RCH HREC within 24-72 hours of occurrence and must be accompanied by a detailed report of the event.**

External SAEs (occurring to participants from other sites) **must be reported in a prompt manner if the information impacts the continued ethical acceptability of the trial or requires documentation to be updated (i.e. protocol or PIS).**

\*An Internal SAE is one occurring in a participant that RCH researchers are responsible for, this is independent of where the event occurs.

HREC Reference #	
Project title	
Principal Investigator	

Date that SAE occurred :	
Date Investigator became aware of SAE :	
Participant ID :	
Internal or External (see above definition):	
Event description and management :	
Event outcome (synopsis):	
Expectedness of the SAE (PI Opinion):	 Expected  Unexpected
Relationship to the study drug	 Unrelated  Possibly related  Probably Related  Definitely Related

Other Comments	
Does the protocol require amending as a result of these SAEs? (If Yes, please submit a modification request with the amended protocol)	 Yes  No
Do the information statements require amending as a result of these SAEs? (If Yes, please submit a modification request with the amended forms)	 Yes  No

Signature	Date
-----------	------

Please submit 1 hard copy with signature OR an electronic copy signed (or emailed) by the PI to [[contact]](mailto:[contact])

**Appendix 13: Categorising severity of AEs related to study treatments: NCI Common Terminology Criteria for AEs (CTCAE)**

Note that AEs not considered to be related to study treatments are not included here. Additionally, note that definitions including self-care and activities of daily living (ADL) must be considered relative to the child's previous level of functional impairment.

Adverse Event	When it may occur	Grade				
		1	2	3	4	5
Blood disorders						
Haemolysis Definition: A disorder characterized by laboratory test results that indicate widespread erythrocyte cell membrane destruction.	
 
• Within 24 hours after infusion
 
• 2-14 days after infusion
 
	Laboratory evidence of haemolysis only (e.g., direct antiglobulin test; DAT; Coombs; schistocytes; decreased haptoglobin)	Evidence of haemolysis and $\geq 2$ gm decrease in haemoglobin.	Transfusion or medical intervention indicated (e.g., steroids)	Life-threatening consequences; urgent intervention indicated	Death
Thrombotic thrombocytopenic Purpura Definition: A disorder characterized by the presence of microangiopathic haemolytic anaemia, thrombocytopenic purpura, fever, renal abnormalities and neurological abnormalities such as seizures, hemiplegia, and visual disturbances. It is an acute or subacute condition.	
 
• 5-12 days after infusion
 
	Evidence of RBC destruction (schistocytosis) without clinical consequences	-	Laboratory findings with clinical consequences (e.g., renal insufficiency, petechiae)	Life-threatening consequences, (e.g., CNS haemorrhage or thrombosis/embolism or renal failure)	Death
Cardiac disorders						
Heart failure Definition: A disorder characterized by the inability of the heart to pump blood at an adequate volume to meet tissue metabolic requirements, or, the ability to do so only at an elevation in the filling pressure.	
 
•
 
	Asymptomatic with laboratory (e.g., BNP [B-Natriuretic Peptide]) or cardiac imaging abnormalities	Symptoms with mild to moderate activity or exertion Severe with symptoms at rest or	Severe with symptoms at rest or with minimal activity or exertion; intervention indicated	Life-threatening consequences; urgent intervention indicated (e.g., continuous IV therapy or mechanical haemodynamic support)	Death
Sinus bradycardia Definition: A disorder characterized by a dysrhythmia with a heart rate less than 60 beats per minute that originates in the sinus node.	
 
• During or immediately after infusion
 
	Asymptomatic, intervention not indicated	Symptomatic, medical intervention indicated	Severe, medically significant, medical intervention indicated	Life-threatening consequences; urgent intervention indicated	Death

Sinus tachycardia A disorder characterized by a dysrhythmia with a heart rate greater than 100 beats per minute that originates in the sinus node.	
 
• During or immediately after infusion
 
	Asymptomatic, intervention not indicated	Symptomatic; non-urgent medical intervention indicated	Urgent medical intervention indicated	-	-
Supraventricular tachycardia Definition: A disorder characterized by a dysrhythmia with a heart rate greater than 100 beats per minute that originates above the ventricles.	
 
• During or immediately after infusion
 
	Asymptomatic, intervention not indicated	Non-urgent medical intervention indicated	Medical intervention indicated	Life-threatening consequences; urgent intervention indicated	Death
Ventricular arrhythmia Definition: A disorder characterized by a dysrhythmia that originates in the ventricles.	
 
• During or immediately after infusion
 
	Asymptomatic, intervention not indicated	Non-urgent medical intervention indicated	Medical intervention indicated	Life-threatening consequences; hemodynamic compromise; urgent intervention indicated	Death
Ventricular tachycardia Definition: A disorder characterized by a dysrhythmia with a heart rate greater than 100 beats per minute that originates distal to the bundle of His.	
 
• During or immediately after infusion
 
	-	Non-urgent medical intervention indicated	Medical intervention indicated	Life-threatening consequences; hemodynamic compromise; urgent intervention indicated	Death
Gastrointestinal disorders						
Diarrhoea	
 
• Diarrhoea includes diarrhoea of small bowel or colonic origin, and/or ostomy diarrhoea.
 
	Increase of <4 stools per day over baseline; mild increase in ostomy output compared to baseline	Increase of 4 – 6 stools per day over baseline; IV fluids indicated <24hrs; moderate increase in ostomy output compared to baseline; not interfering with ADL	Increase of ≥7 stools per day over baseline; incontinence; IV fluids ≥ 24 hrs; hospitalization; severe increase in ostomy output compared to baseline; interfering with ADL	Life-threatening consequences (e.g., hemodynamic collapse)	Death
Mucositis / stomatitis	
 
• Mucositis/stomatitis (functional/symptomatic) may be used for identifying GvHD.
 
	Erythema of the mucosa	Patchy ulcerations or pseudo-membranes	Confluent ulcerations or pseudo-membranes; bleeding with minor trauma	Tissue necrosis; significant spontaneous bleeding; life-threatening consequences	Death

Nausea Definition: A disorder characterized by a queasy sensation and/or the urge to vomit.	
 
• During or immediately after infusion
 
• May be early indication of allergic reaction or anaphylaxis
 
	Loss of appetite without alteration in eating habits	Oral intake decreased without significant weight loss, dehydration or malnutrition	Inadequate oral caloric or fluid intake; tube feeding, TPN, or hospitalization indicated	-	-
Vomiting Definition: A disorder characterized by the reflexive act of ejecting the contents of the stomach through the mouth.	
 
• During or immediately after infusion
 
• May be early indication of allergic reaction or anaphylaxis
 
	1 - 2 episodes (separated by 5 minutes) in 24 hrs	3 - 5 episodes (separated by 5 minutes) in 24 hrs	≥6 episodes (separated by 5 minutes) in 24 hrs; tube feeding, TPN or hospitalization indicated	Life-threatening consequences; urgent intervention indicated	Death
General disorders and administration site conditions						
Chills Definition: A disorder characterized by a sensation of cold that often marks a physiologic response to sweating after a fever.	
 
• During or immediately after infusion
 
• Within 36 hours of infusion
 
	Mild sensation of cold; shivering; chattering of teeth	Moderate tremor of the entire body; narcotics indicated	Severe or prolonged, not responsive to narcotics	-	-
Fever Definition: A disorder characterized by elevation of the body's temperature above the upper limit of normal.	
 
• During or immediately after infusion
 
• Within 36 hours of infusion
 
	38.0 - 39.0 °C	>39.0 - 40.0 °C	>40.0 °C	>40.0 °C for >24 hrs	Death
Headache Definition: A disorder characterized by a sensation of marked discomfort in various parts of the head, not confined to the area of distribution of any nerve.	
 
• During or immediately after infusion
 
• Up to 36 hours after infusion
 
	Mild pain	Moderate pain; limiting instrumental ADL	Severe pain; limiting self-care ADL	-	-
Infusion related reaction Definition: A disorder characterized by adverse reaction to the infusion of pharmacological or biological substances.	
 
• During or immediately after infusion
 
	Mild transient reaction; infusion interruption not indicated; intervention not indicated	Therapy or infusion interruption indicated but responds promptly to symptomatic treatment (e.g., antihistamines, NSAIDS, narcotics, IV fluids); prophylactic medications indicated for ≤24hrs	Prolonged (e.g., not rapidly responsive to symptomatic medication and/or brief interruption of infusion); recurrence of symptoms following initial improvement; hospitalization indicated for clinical sequelae	Life-threatening consequences; urgent intervention indicated	Death


Infusion site extravasation Definition: A disorder characterized by leakage of a pharmacologic or a biologic substance from the infusion site into the surrounding tissue. Signs and symptoms include induration, erythema, swelling, burning sensation and marked discomfort at the infusion site.
	
 
• During or immediately after infusion
 
	-	Erythema with associated symptoms (e.g., edema, pain, induration, phlebitis)	Ulceration or necrosis; severe tissue damage; operative intervention indicated	Life-threatening consequences; urgent intervention indicated	Death

Injection site reaction Definition: A disorder characterized by an intense adverse reaction (usually immunologic) developing at the site of an injection.
	
 
• During or immediately after infusion
 
	Tenderness with or without associated symptoms (e.g., warmth, erythema, itching)	Pain; lipodystrophy; oedema; phlebitis	Ulceration or necrosis; severe tissue damage; operative intervention indicated	Life-threatening consequences; urgent intervention indicated	Death

Irritability Definition: A disorder characterized by an abnormal responsiveness to stimuli or physiological arousal; may be in response to pain, fright, a drug, an emotional situation or a medical condition.
	
 
•
 
	Mild; easily consolable	Moderate; limiting instrumental ADL; increased attention indicated	Severe abnormal or excessive response; limiting self-care ADL; inconsolable	-	-

Localized oedema Definition: A disorder characterized by swelling due to excessive fluid accumulation at a specific anatomic site.
	
 
• Within 24 hours of infusion
 
• Pulmonary oedema may be indication of transfusion-associated circulatory overload (TACO)
 
	Localized to dependent areas, no increased disability or functional impairment	Moderate localized oedema and intervention indicated; limiting instrumental ADL	Severe localized oedema and intervention indicated; limiting self-care ADL	-	-

Non-cardiac chest pain Definition: A disorder characterized by discomfort in the chest unrelated to a heart disorder.
	
 
• During or immediately after infusion
 
	Mild pain	Moderate pain; limiting instrumental ADL	Severe pain; limiting self-care ADL	-	-

Pain Definition: A disorder characterized by the sensation of marked discomfort, distress or agony.
	
 
• During or immediately after infusion
 
	Mild pain	Moderate pain; limiting instrumental ADL	Severe pain; limiting self-care ADL	-	-
Immune system						

Allergic reaction Definition: A disorder characterized by an adverse local or general response from exposure to an allergen.
	
 
• During or immediately after infusion
 
	
Transient flushing or rash, drug fever <38°C; intervention not indicated
	
Intervention or infusion interruption indicated; responds promptly to symptomatic treatment (e.g., antihistamines, NSAIDS, narcotics); prophylactic medications indicated for ≤24 hrs
	
Prolonged (e.g., not rapidly responsive to symptomatic medication and/or brief interruption of infusion); recurrence of symptoms following initial improvement; hospitalization indicated for clinical sequelae (e.g., renal impairment, pulmonary infiltrates)
	
Life-threatening consequences; urgent intervention indicated
	
Death

Anaphylaxis Definition: A disorder characterized by an acute inflammatory reaction resulting from the release of histamine and histamine-like substances from mast cells, causing a hypersensitivity immune response. Clinically, it presents with breathing difficulty, dizziness, hypotension, cyanosis and loss of consciousness and may lead to death.
	
 
• During or immediately after infusion
 
	
-
	
-
	
Symptomatic bronchospasm, with or without urticaria; parenteral intervention indicated; allergy-related oedema/angioedema; hypotension
	
Life-threatening consequences; urgent intervention indicated
	
Death


Cytokine release syndrome Definition: A disorder characterized by nausea, headache, tachycardia, hypotension, rash, and shortness of breath; it is caused by the release of cytokines from the cells.
	
 
•
 
	
Mild reaction; infusion interruption not indicated; intervention not indicated
	
Therapy or infusion interruption indicated but responds promptly to symptomatic treatment (e.g., antihistamines, NSAIDS, narcotics, IV fluids); prophylactic medications indicated for ≤24 hrs
	
Prolonged (e.g., not rapidly responsive to symptomatic medication and/or brief interruption of infusion); recurrence of symptoms following initial improvement; hospitalization indicated for clinical sequelae (e.g., renal impairment, pulmonary infiltrates)
	
Life-threatening consequences; pressor or ventilatory support indicated
	
Death

Infection
						

Catheter related infection Definition: A disorder characterized by an infectious
	
 
• Within 24 hours of infusion
 
	
-
	
Localized; local intervention indicated; oral
	
IV antibiotic, antifungal, or antiviral intervention indicated; radiologic or
	
Life-threatening consequences;
	
Death

process that arises secondary to catheter use.			intervention indicated (e.g., antibiotic, antifungal, antiviral)	operative intervention indicated	urgent intervention indicated	
Respiratory infection Definition: A disorder characterized by an infectious process involving the respiratory tract.	• Throughout study	-	Moderate symptoms; oral intervention indicated (e.g., antibiotic, antifungal, antiviral)	IV antibiotic, antifungal, or antiviral intervention indicated; radiologic, endoscopic, or operative intervention indicated	Life-threatening consequences; urgent intervention indicated	Death
Procedural complications						
Bruising Definition: A finding of injury of the soft tissues or bone characterized by leakage of blood into surrounding tissues.	• During or immediately after needle	Localized or in a dependent area	Generalized	-	-	-
Venous injury Definition: A finding of damage to a vein.	• During or immediately after needle	Asymptomatic diagnostic finding; intervention not indicated	Symptomatic (e.g., claudication); repair or revision not indicated	Severe symptoms; limiting self-care ADL; repair or revision indicated; disabling	Life-threatening consequences; evidence of end organ damage; urgent operative intervention indicated	Death
Psychiatric disorders						
Agitation Definition: A disorder characterized by a state of restlessness associated with unpleasant feelings of irritability and tension.	• During or immediately after infusion May be early indication of anaphylaxis	Mild mood alteration	Moderate mood alteration	Severe agitation; hospitalization not indicated	Life-threatening consequences; urgent intervention indicated	Death
Anxiety Definition: A disorder characterized by apprehension of danger and dread accompanied by restlessness, tension, tachycardia, and dyspnea unattached to a clearly identifiable stimulus.	• Throughout study	Mild symptoms; intervention not indicated	Moderate symptoms; limiting instrumental ADL	Severe symptoms; limiting self-care ADL; hospitalization not Indicated	Life-threatening; hospitalization indicated	Death
Confusion Definition: A disorder characterized by a lack of clear and orderly thought and behaviour.	•	Mild disorientation	Moderate disorientation; limiting instrumental ADL	Severe disorientation; limiting self-care ADL	Life-threatening consequences; urgent intervention indicated	Death

Depression Definition: A disorder characterized by melancholic feelings of grief or unhappiness.	
 
Throughout study
 
	Mild depressive symptoms	Moderate depressive symptoms; limiting instrumental ADL	Severe depressive symptoms; limiting self-care ADL; hospitalization not indicated	Life-threatening consequences, threats of harm to self or others; hospitalization indicated	Death
Restlessness Definition: A disorder characterized by an inability to rest, relax or be still.	
 
During or immediately after infusion May be early indication of anaphylaxis
 
	Mild symptoms; intervention not indicated	Moderate symptoms; limiting instrumental ADL	Severe symptoms; limiting self-care ADL	-	-
Renal and urinary disorders						
Haemoglobinuria Definition: A disorder characterized by laboratory test results that indicate the presence of free haemoglobin in the urine.	
 
During or immediately after infusion
 
Within 36 hours of infusion
 
	Asymptomatic; clinical or diagnostic observations only; intervention not indicated	-	-	-	-
Respiratory, thoracic and mediastinal disorders						
Bronchospasm Definition: A disorder characterized by a sudden contraction of the smooth muscles of the bronchial wall.	
 
During or immediately after infusion
 
	Mild symptoms; intervention not indicated	Symptomatic; medical intervention indicated; limiting instrumental ADL	Limiting self-care ADL; oxygen saturation decreased	Life-threatening respiratory or hemodynamic compromise; intubation or urgent intervention indicated	Death
Dyspnea Definition: A disorder characterized by an uncomfortable sensation of difficulty breathing.	
 
During or immediately after infusion
 
	Shortness of breath with moderate exertion	Shortness of breath with minimal exertion; limiting instrumental ADL	Shortness of breath at rest; limiting self-care ADL	Life-threatening consequences; urgent intervention indicated	Death
Hypoxia Definition: A disorder characterized by a decrease in the level of oxygen in the body.	
 
During or immediately after infusion
 
	-	Decreased oxygen saturation with exercise (e.g., pulse oximeter <88%); intermittent supplemental oxygen	Decreased oxygen saturation at rest (e.g., pulse oximeter <88% or PaO 2 ≤55 mm Hg)	Life-threatening airway compromise; urgent intervention indicated (e.g., tracheotomy or intubation)	Death
Respiratory failure Definition: A disorder characterized by impaired gas exchange by the respiratory system resulting in hypoxemia and a decrease in oxygenation	
 
During or immediately after infusion
 
	-	-	-	Life-threatening consequences; urgent intervention, intubation, or ventilatory support indicated	Death

of the tissues that may be associated with an increase in arterial levels of carbon dioxide.						

Stridor Definition: A disorder characterized by a high pitched breathing sound due to laryngeal or upper airway obstruction.
	
 
• During or immediately after infusion
 
	-	-	Respiratory distress limiting self-care ADL; medical intervention indicated	Life-threatening airway compromise; urgent intervention indicated (e.g., tracheotomy or intubation)	Death

Wheezing Definition: A disorder characterized by a high-pitched, whistling sound during breathing. It results from the narrowing or obstruction of the respiratory airways.
	
 
• During or immediately after infusion
 
	Detectable airway noise with minimal symptoms	Moderate symptoms; medical intervention indicated; limiting instrumental ADL	Severe respiratory symptoms limiting self-care ADL; oxygen therapy or hospitalization indicated	Life-threatening consequences; urgent intervention indicated	Death
Skin and subcutaneous tissue disorders						
Rash/desquamation	
 
• Rash/desquamation may be used for identifying GvHD
 
	Macular or popular eruption or erythema without associated symptoms	Macular or popular eruption or erythema with pruritus or other associated symptoms; localized desquamation or other lesions covering <50% of body surface area (BSA)	Severe, generalized erythroderma or macular, papular or vesicular eruption; desquamation covering ≥50% BSA	Generalized exfoliative, ulcerative, or bullous dermatitis	Death

Urticaria Definition: A disorder characterized by an itchy skin eruption characterized by wheals with pale interiors and well-defined red margins.
	
 
• During or immediately after infusion
 
• May be early indication of allergic reaction or anaphylaxis
 
	Urticarial lesions covering <10% BSA; topical intervention indicated	Urticarial lesions covering 10-30% BSA; oral intervention indicated	Urticarial lesions covering >30% BSA; IV intervention indicated	-	-
Vascular disorders						

Hypertension Definition: A disorder characterized by a pathological increase in blood pressure; a repeatedly elevation in the blood pressure exceeding 140 over 90 mm Hg.
	
 
• During or immediately after infusion
 
• Within 36 hours of infusion
 
	Prehypertension (systolic BP 120 - 139 mm Hg or diastolic BP 80 - 89 mm Hg)	Stage 1 hypertension BP >ULN medical intervention indicated; recurrent or persistent (≥24hrs)	Stage 2 hypertension (systolic BP ≥160 mm Hg or diastolic BP ≥100 mm Hg); medical intervention indicated; more than one drug or more intensive therapy	Life-threatening consequences (e.g., malignant hypertension, transient or permanent neurologic deficit, hypertensive crisis);	Death

				than previously used indicated	urgent intervention indicated	
Hypotension Definition: A disorder characterized by a blood pressure that is below the normal expected for an individual in a given environment.	
 
• During or immediately after infusion
 
• Within 36 hours of infusion
 
	Asymptomatic, intervention not indicated	Non-urgent medical intervention indicated	Medical intervention or hospitalization indicated	Life-threatening and urgent intervention indicated	Death

Graft versus Host Disease [63]

Stage	Skin	Liver (bilirubin)	Gut (stool output per day)
0	No GVHD rash	< 2mg/dl	Child: < 10 ml/kg/day or persistent nausea
1	Maculopapular rash 25% BSA	2–3 mg/dl	Child: 10–19.9 ml/kg/day or persistent nausea, vomiting or anorexia, with a positive upper GI biopsy
2	Maculopapular rash 25–50% BSA	3.1–6 mg/dl	Child: 20–30 ml/kg/day
3	Maculopapular rash > 50% BSA	6.1–15mg/dl	Child: > 30 ml/kg/day
4	Generalized erythroderma plus bullous formation	> 15mg/dl	Severe abdominal pain with or without ileus
Grade			
I	Stages 1–2	None	None
II	Stage 3 or	Stage 1 or	Stage 1
III	—	Stages 2–3 or	Stages 2–4
IV	Stage 4 or	Stage 4	—

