#### 4.4. Eligibility Criteria

##### *Inclusion Criteria*

To be eligible for this study, the following criteria must be fulfilled:

- Aged older than 1 year and younger than 16 years at time of enrolment
- Diagnosis of any type of CP
- CP of any severity
- A record of sibling CBU in storage at a TGA accredited private cord blood bank
- Ability to travel to one of the trial centres
- Ability to participate in assessments
- Informed consent by parent/guardian and an indication of willingness/compliance by children

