#### Observation

Vital signs will be monitored by the nurse prior to UCBC infusion, during the infusion, every 15 minutes for 1 hour, then every 30 minutes for 2 hours. The monitoring will include temperature measurement (in °C), blood pressure (in mmHg), pulse oximetry (in % oxygen saturation) and checks for nausea and discomfort.

Participants will also be monitored for symptoms of toxicity, including nausea, fever, chills, and for symptoms of anaphylaxis including wheezing and urticaria.

A transplant physician will be available and called if vital signs fall outside the normal range (see section 8) or if there are signs of an adverse event.

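### Appendix 13 defines heart-rate adverse events by fixed limits with no age or baseline reference, so a trivial rise in a young child can enter the 36-hour AE proportion; its hypertension row does not agree with itself

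*Protocol*

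**What the plan says.** Section 4.4 admits children "Aged older than 1 year and younger than 16 years at time of enrolment". Section 8 makes Appendix 13 the tool for grading adverse events.

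**Heart rate.** Sinus tachycardia is "A disorder characterized by a dysrhythmia with a heart rate greater than 100 beats per minute"; sinus bradycardia is "A disorder characterized by a dysrhythmia with a heart rate less than 60 beats per minute that originates in the sinus node". In both rows Grade 1 is the asymptomatic case with no intervention needed. Neither row mentions age or the child's own earlier rate.

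**Blood pressure.** Hypertension is described as "a repeatedly elevation in the blood pressure exceeding 140 over 90 mm Hg". Its Grade 1 is 120–139 systolic or 80–89 diastolic, Grade 2 refers to a pressure above the upper limit of normal, and Grade 3 starts at 160 systolic or 100 diastolic. Hypotension is instead "a blood pressure that is below the normal expected for an individual in a given environment".

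**Other rows.** Diarrhoea is graded by the increase over baseline. The appendix's introductory note says that definitions involving self-care and daily living "must be considered relative to the child's previous level of functional impairment". That note does not extend to heart rate or blood pressure.

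**Use in the results.** Section 4.3 makes AEs and vital signs from infusion to 36 hours part of the primary safety outcome. Section 9 summarises safety as the proportion of participants with an SAE and with an AE in each window, with no minimum grade.

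**Normal range.** Section 7.1 (Observation) says that a transplant physician is "called if vital signs fall outside the normal range (see section 8"). Section 5.5 makes the same reference.

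**The concern.** One limit serves a toddler and an adolescent alike, and the lowest grade asks for nothing beyond the rate itself. If the youngest participants ordinarily have rates near 100/min, a rise of a few beats during cannulation, hydration or infusion carries them over the line. Such a child then counts as having had an AE in the first primary window. With 12 treated children, a few of these would make the reported proportion partly a reflection of the age mix, and two hospitals could classify the same reading differently.

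For blood pressure the risk runs the other way. Fixed hypertension figures may be too high to register a genuine rise in a small child. Section 5.5 gives six hours of intravenous fluid and itself watches for hypertension, so this event is one that the trial needs to detect.

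**Working it through.** **1. Denominator.** Section 9 gives groups of 3, 3 and 6: 3 + 3 + 6 = 12. The stated 12 is reproduced.

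**2. What each Appendix 13 row is compared with.**
- Sinus tachycardia: above 100/min, fixed.
- Sinus bradycardia: below 60/min, fixed.
- Hypertension: 140/90 in the definition; fixed figures in Grades 1 and 3; an unnamed upper limit of normal in Grade 2.
- Hypotension: the individual's expected normal.
- Diarrhoea: the child's baseline.
- Self-care and daily-living items: the child's previous level.

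The appendix already uses an individual reference in several places, but not for heart rate.

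**3. Does Section 8 close the gap?** Section 8 limits AEs to those that begin or worsen during the trial, and recording starts at infusion. A usual rate that has not changed is therefore not an AE. A child who goes from 98 to 104/min (illustrative figures), a rise of 6 beats, newly meets the tachycardia description and fits Grade 1. No text says how large a change must be or which reading it is compared with.

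**4. Size in the 36-hour proportion.** Let k be the number of children counted only because of such a rise, and p the proportion who would otherwise have an AE. The expected proportion is (k + (12 − k)p)/12, so each extra child adds (1 − p)/12, at most 1/12 = 8.3 points.

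For p, Section 2.1 reports two autologous studies, used here only as illustrative levels: 3/184 = 1.6% and 5/20 = 25%.

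| k | p = 3/184 | p = 5/20 |
|---|---|---|
| 0 | 1.6% | 25.0% |
| 1 | 9.8% | 31.2% |
| 3 | 26.2% | 43.8% |
| 6 | 50.8% | 62.5% |

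For example, with k = 3 and p = 3/184: (3 + 9 × 0.0163)/12 = 0.262. One child adds (1 − 0.0163)/12 = 8.2 points at the lower background and (1 − 0.25)/12 = 6.25 points at the higher.

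If each child independently has chance q of being counted in this way, the chance of at least one among 12 is 1 − (1 − q)^12: 71.8% for q = 0.10, 96.8% for q = 0.25, and over 99.9% for q = 0.50. Both k and q are assumptions; the protocol gives no paediatric heart rates and no age distribution.

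**5. Hypertension row.** A pressure with both components in the Grade 1 bands (at most 139 and 89) does not exceed 140/90, so it fails the row's own definition. Grade 2 depends on a limit that is not named. A child whose usual systolic pressure is s can rise by up to 120 − s without reaching Grade 1 on the systolic figure; the lower s is, the larger the rise that goes ungraded. The protocol gives no values for s.

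**6. Normal range.** Section 8 covers definitions, eliciting, documenting and reporting of events, and contains no vital-sign range. Its only route to such figures is Appendix 13, which leads back to the fixed limits.

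**The case against.** The strongest reply is that Section 8 already solves the problem: an AE must be untoward, must begin or worsen in the trial, and is evaluated by a study doctor. Appendix 13 grades severity and is not a detection rule; its rows speak of a disorder, not a single reading, and nothing says that every value over 100/min is recorded automatically. The observation list in Section 7.1 does not even name heart rate; pulse appears under physical examination.

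Much of this stands. A reader might infer that a young child's ordinary resting rate becomes an AE by itself, and might size the problem by the share of children already above 100/min before infusion. Section 8 does not support that reading. What the reply leaves open is a small rise: the doctor has one number, no comparator, and a Grade 1 that needs no symptom.

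A reader might also infer that ordinary blood pressures would be counted as AEs. The documents do not support this either. Hypotension is judged against the individual, hypertension Grade 2 does not use a fixed figure, and if young children's usual pressures lie below the fixed ones, the error is an under-count.

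It is also fair that results are descriptive, that severity and likely relation to treatment are documented for each AE, and that an asymptomatic Grade 1 rate is neither automatically an SAE nor the stated GvHD stopping criterion. An analysis plan could add baseline-referenced summaries, but it would not change the protocol's own grading table, which is applied when the event is recorded.

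**Conclusion.** The concern holds for heart rate in a limited form: fixed limits, no stated comparison with baseline, and a symptom-free Grade 1 together allow a trivial rise to be counted in the 36-hour AE proportion, at up to 8.3 points per child of 12. This rests on the assumption that some young participants have usual rates near or above 100/min, which the protocol neither gives nor excludes. How many children would be affected cannot be derived from it.

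For hypertension the finding is a definition that its own grades contradict and a limit left unnamed. The likely consequence is a missed or under-graded rise, again on the assumption that small children's usual pressures are lower than the fixed figures. Hypotension needs no change.

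The missing normal range in Section 8 is a plain cross-reference fault that needs no assumption. It concerns when a physician is called rather than how AEs are counted.

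None of this affects a test or a numerical stopping boundary. It affects how far the primary descriptive proportion can be read as an effect of the infusion.

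**What to change.** 1. In Appendix 13, state that heart-rate and hypertension events are classified either as a change from the child's own pre-infusion reading or against one named age-specific reference used at both infusion hospitals. This extends the individual or baseline reference that the appendix already uses for hypotension and diarrhoea. Add a footnote recording the departure from the literal CTCAE definitions.
2. Reconcile the hypertension definition with its Grades 1 to 3, and name the source of the upper limit of normal.
3. Reconcile the references in Sections 5.5 and 7.1 with Section 8, so that the normal range they cite exists somewhere.

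Which limits or size of change to use is for the clinical investigators; none is suggested here.

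The cost is appendix wording and one comparison on the case report form. Blood pressure is already taken before infusion (Section 7.1). Pulse is part of the pre-infusion physical examination, and Section 6 schedules an examination at Visit 3. The drawback is slightly less direct comparability with studies that apply the CTCAE wording unchanged, which the footnote makes visible.
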